5.3 STUDY POPULATION

5.3.1 SAMPLE SIZE CALCULATION

The sample size calculation was based on "lens handling at removal" using historical data at 1 week in which participants used a 0-100 scale (100 being best).

A sample size of 64 is required to detect a mean difference in "handling at removal" of 10 units on a 0 to 100 scale using a standard deviation of the paired differences of 24.2 with 90% power and alpha 0.05 in a two-tailed t-test. Therefore, up to 73 participants will be dispensed with study products with the goal to complete at least 64.

Power and Sample Size (handling on removal (0-100)

Paired t Test
Testing mean paired difference = 0 (versus ≠ 0)
Calculating power for mean paired difference = difference
α = 0.05 Assumed standard deviation of paired differences = 24.2

Results

Difference	Sample Size	Target Power	Actual Power
10	48	0.80	0.800662
10	54	0.84	0.846406
10	64	0.90	0.902344

Figure 1: Sample size calculation graph

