5.3.2 NUMBER OF PARTICIPANTS

Participants will be recruited using site records, databases and advertising materials (eg. posters, email scripts) approved by the ethics review board. All initial individual-targeted recruitment activities, such as any direct mailing of recruitment scripts, will be conducted by practice staff that are not directly involved in conducting the research. This separation will reduce any undue influence of the optometrist-patient relationship. This process will also eliminate opportunity for the investigator to access personal health information before any consent for disclosure is provided by the potential participant.

It is anticipated that up to 73 potential participants may attend a Screening visit and up to 70 participants may be randomized and dispensed with study products, with a target of at least 64 completing the study.

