10 DEVICE MALFUNCTIONS

A device malfunction means the failure of the device to meet its performance specification or otherwise perform as intended. Any defective lens that is *likely* to cause or contribute to a *Serious Adverse Event* should be reported to CORE and the sponsor **within 24 hours** of the investigator becoming aware of the malfunction. Sterling IRB would also be notified within 24 hours of any device malfunction that may contribute to a *Serious Adverse Event*.

Other defective lenses should be reported to CORE as soon as possible (usually in weekly study updates).

This clinical study will also ascertain satisfaction or preference with subjective attributes such as comfort, vision, or lens handling. Responses to these subjective questionnaires will not be considered as complaints or device malfunctions.

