12 STATISTICAL ANALYSIS AND DATA MANAGEMENT

12.1 STATISTICAL ANALYSIS

All data will be analyzed by CORE at the University of Waterloo. Unmasked data analysis will be conducted using Statistica 10, Statsoft or other suitable software. Descriptive statistics will be provided on demographic data (age, gender, refractive error distribution, etc.). Table 7 lists the primary and other outcome variables and anticipated statistical procedures.

Visual acuity results will be converted to LogMAR for analysis purposes.

Comparisons will be made between the study lenses for the variables measured at the 1-week visits. Additionally the subjective ratings completed on days 1, 3 and 6 with each study lens will be compared for differences and equivalence. A binomial test will be used to analyze the results for the count data of subjective preferences and experience responses. Where relevant, the number of "no preference" responses will be evenly distributed to the two options on the basis they would be equally likely to choose either.

For assessments conducted for each eye separately, the right eye will be used for analysis. If a general difference is found (paired t-test / Wilcoxon matched pairs) between OD and OS, a comment will be provided

Where appropriate, data may be presented as both mean and as counts by 'bucket' groups.

Additional analysis may be conducted

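### Splitting 'no preference' answers evenly before a binomial test makes the preference test conservative once about a fifth of participants are undecided

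*Combined protocol and SAP*

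**What the plan says.** On preferences, section 12.1 states: "A binomial test will be used to analyze the results for the count data of subjective preferences and experience responses". The next sentence says that, where relevant, the 'no preference' "responses will be evenly distributed to the two options on the basis they would be equally likely to choose either". Read together, the counts that enter the test are those after the split.

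The visible text does not say when the split is relevant, what happens to the leftover answer when the undecided number is odd, whether the test is exact, or what alpha applies. It gives no expected 'no preference' rate. Table 7, to which section 12.1 refers for outcomes and procedures, and the questionnaire items are not visible in the public copy. It therefore cannot be checked which items offer 'no preference' or whether all three counts are also reported.

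Preference is a stated aim in section 10: "This clinical study will also ascertain satisfaction or preference with subjective attributes such as comfort, vision, or lens handling". The number of respondents depends on completion. Section 5.3.1 says "up to 73 participants will be dispensed with study products with the goal to complete at least 64", while section 5.3.2 says "up to 70 participants may be randomized and dispensed with study products, with a target of at least 64 completing the study". The range 64 to 73 covers both.

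**The concern.** The plan's reason for the split is that undecided participants would be equally likely to choose either lens. If they really were made to choose at random, their choices would vary from sample to sample as a binomial count does. Assigning exactly half to each lens removes that variation but keeps those people in the denominator. The test then measures the difference between lenses against too large a variance.

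At stake is the reporting of preferences for comfort, vision and handling. Where many participants are undecided, a real preference among the others is more likely to be reported as not significant. The strictness of the test would also differ from item to item with the undecided share, so p-values across items would not be comparable.

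**Working it through.** **The plan's own figure.** The only calculation in the documents is for the primary paired t-test. With difference 10, SD 24.2 and n = 64, the noncentrality is 10/(24.2/√64) = 3.306 and two-sided power at alpha 0.05 is 0.9023, as stated. For n = 48 and 54 the power is 0.8007 and 0.8464, also as stated. There is no figure for the preference test to reproduce.

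**Inputs.** N is 64 to 73 (sections 5.3.1 and 5.3.2). Assumed: null proportion 0.5; two-sided alpha 0.05, as for the primary test; undecided share q from 5% to 50%; true preference among deciders 70:30 or 75:25.

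**Variance.** Let T of N be undecided and X of the other N−T choose lens A. The split count is S = X + T/2. Under the null X ~ Bin(N−T, ½), so Var(S) = (N−T)/4. The test treats S as Bin(N, ½), with variance N/4. The ratio of true to assumed variance is 1−t, where t = T/N. The large-sample type I error of a nominal 5% test is 2[1−Φ(1.96/√(1−t))]: 3.9% at t = 10%, 2.8% at 20%, 1.9% at 30% and 0.6% at 50%.

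**Exact enumeration.** T ~ Bin(N, q) and X ~ Bin(N−T, p). The split test is an exact binomial test of S out of N, with an odd leftover answer placed at random. The comparison is an exact test of X out of N−T. Reject at p ≤ 0.05.

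| N = 64, split v undecided excluded | 20% undecided | 30% | 50% |
|---|---|---|---|
| Type I error | 1.7% v 3.7% | 1.1% v 3.6% | 0.3% v 3.1% |
| Power, 70:30 | 70% v 80% | 56% v 74% | 22% v 56% |

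With nobody undecided, the exact test at N = 64 has a type I error of 3.3%, so discreteness explains only part of the shortfall.

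| Range over N = 64 to 73 | 20% undecided | 30% | 50% |
|---|---|---|---|
| Type I error, split | 1.5–2.9% | 0.9–1.9% | 0.2–0.6% |
| Type I error, excluded | 3.7% | 3.6–3.7% | 3.1–3.3% |
| Power lost, 70:30 (points) | 3.3–10.9 | 9.4–19.2 | 26.1–37.0 |
| Power lost, 75:25 (points) | 1.3–4.4 | 4.9–10.7 | 24.5–36.8 |
| Power lost, 70:30, odd leftover to leading lens | 1.3–8.5 | 6.6–16.2 | 22.9–34.2 |
| Power lost, 70:30, uncorrected normal test | 4.7–8.5 | 11.1–16.0 | 31.2–36.8 |

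**Example.** Take 29 v 15 with 20 undecided. Testing 29 of 44 gives exact p = 0.049. After the split the counts are 29 + 10 = 39 and 15 + 10 = 25, and 39 of 64 gives p = 0.103.

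**Few undecided.** At 10% undecided and 70:30, the exact-test change runs from a 5.1-point loss (N = 69) to a 0.5-point gain (N = 67). At 5% it runs from a 3.7-point loss to a 1.1-point gain.

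**Direction.** Over N = 64 to 73, 11,750 possible tables have an even, non-zero undecided number. With the exact test the split gains significance in none of them and loses it in 1,206. In the 12,095 tables with an odd number, giving the leftover to the leading lens gains significance in 20 (never with more than 7 undecided) and loses it in 962. One such gain is 40 v 24 with 1 undecided: p = 0.060 for 40 of 64 becomes 0.046 for 41 of 65. Under that rule type I error can just pass 5% (5.2% at N = 67 with 5% undecided).

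**The case against.** The strongest objection is about weight. Preference is not the primary outcome, and neither the sample size nor any visible decision rule rests on it. With an odd leftover placed at random, type I error stays below 5% at every N and undecided rate examined (at most 4.5%), so the fault is lost efficiency and not false claims. The undecided rate in this trial is unknown. At 20% the loss can be as small as 3.3 points at 70:30 or 1.3 at 75:25, and the N = 64 figure lies near the top of its range. The largest losses need half the sample to be undecided. Table 7 may hold further rules. No document says that a leftover answer goes to the leading lens. The split also has a purpose: it keeps the result on the scale of all respondents.

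Most of this stands as a limit on size. The 20% mark is a judgement about when the loss matters, since the variance is overstated at any undecided share above zero. The leading-lens rule is only one possible reading of a gap in the visible text. None of it repairs the test, which uses a variance that its own counts cannot have. The all-respondent scale can be kept by reporting the three counts, without testing the split total.

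**Conclusion.** The concern holds. Testing the evenly split total as binomial overstates the null variance by a factor of N/(N−T), and the test is clearly conservative from about 20% undecided upwards. For a 70:30 preference and an exact test over N = 64 to 73, the loss against testing stated preferences is 3.3–10.9 points at 20% undecided, 9.4–19.2 at 30% and 26.1–37.0 at 50%. At 10% or less the effect is small and of uncertain sign.

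The variance argument needs no assumption about this trial. The size rests on assumed undecided rates, preference strengths, alpha and form of test. A secondary point is that, with an exact test and very few undecided, a result near 0.05 can turn on how one leftover answer is assigned. The Day 6 handling rating, its analysis and the sample size are untouched. This should be fixed, as an error in a secondary analysis.

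**What to change.** In section 12.1, replace the even-split sentence with: 'The binomial (sign) test will be done on participants who state a preference; the numbers and percentages preferring each lens and with no preference will be reported for all respondents.' State whether the test is exact. An evenly split percentage may stay as a description but should not be tested. The odd leftover answer then no longer affects any p-value.

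The cost is one sentence and no extra data. The test has a smaller stated n, and the 'no preference' share must appear beside each p-value so that a share among deciders is not read as a share of everyone. With very few undecided, exclusion can cost a little exact-test power at some N. At 70:30 and 5% undecided this is at most 1.1 points against a randomly placed leftover, or 2.4 points against giving it to the leading lens.

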12.2 DATA MANAGEMENT

Data will be collected and written on paper forms which will be provided to each site by CORE. Each site will be instructed to send completed study forms to CORE using a secure file share system operated by the University of Waterloo called Sendit which uses 128bit (or 256bit) SSL encryption. The sites will receive their individual accounts and passwords.

The site will endeavour to send the scanned forms to CORE on the same day as the study visit or a maximum of two days after the study visit.

Within CORE, data will be entered into a REDCap database developed and tested specifically for this study and accessible only to trained, authorised users. A data management plan will be developed to describe the data handling in more detail, including the personnel involved.

Data from this study will be retained by CORE for a minimum of 25 years on a passwordprotected server. After 25 years, data will be disposed of in accordance with the guidelines laid out by the University of Waterloo. More details regarding storage procedures are provided in section 15.7 and also in CORE SOP014 Clinical data management.

At the completion of the study CORE will provide a copy of the study database in Excel format to the sponsor when requested. Data will typically be sent using Sendit. This system provides a secure way to transfer files when email is not appropriate, whether because of file size, file type or concerns over security. Sendit includes features such as password protection, a restricted time period for download, IP logging and email notification of download. Files may be encrypted prior to transmission at the request of the sponsor. Using this method means that data files are only stored on University of Waterloo servers during the transfer.

12.3 COMMENTS ON SOURCE DOCUMENTS

Data analysis will not be conducted on comments which have been recorded in the source documents. Only relevant and applicable comments will be included in the final report as deemed necessary by CORE's Lead Co-ordinator.

13 PROTOCOL & OTHER TRAINING

All study personnel will be required to complete training prior to their involvement in the study. This will include training by CORE on the study protocol, study procedures, informed consent procedures, and on the randomization and participant masking procedures, as well as training for Good Clinical Practice. All site Principal Investigators and co-investigators will provide a scan of their curriculum vitae, license to practice optometry and evidence of professional indemnity insurance. Additional training and site qualification may be required as indicated by the sponsor.

14 STUDY MONITORING

Each site will provide regular status reports to CORE. Status reports will include:

- The number of participants screened, enrolled, and randomized (i.e. assigned a study ID number), discontinued and completed.
- Details of all protocol deviations, adverse events, device malfunctions.
- Reports of unintended events.

CORE will collate the site updates and provide 2-weekly status reports to the study sponsor.

Study monitoring visits to the sites may be conducted by CORE, the sponsor, or sponsor's designate, throughout the study and will be scheduled in conjunction with the Principal Investigator at each site. In addition study records may be inspected by the sponsor, the sponsor's designate, Sterling Institutional Review Board, and by regulatory authorities in Canada and the United States, namely Health Canada and the United States Food and Drug Administration (FDA); however, they will not be permitted to take away any records containing identifiable personal information.

Study data review and data monitoring will be conducted by CORE personnel. To improve data integrity, data entry will be conducted by one person and a second person will visually compare the data entry to the source documents. Data queries will be reported to the site within 5 working days of receipt of initial data. A response resolving the query will be expected from the site within 5 working days of receipt of the query.

All adverse events and protocol deviations will be reviewed by the site Principal Investigator and CORE's Lead Coordinator. All serious adverse events and major protocol deviations will be reviewed by the site Principal Investigator and CORE's Director and/or Head of Clinical Research.

15 STUDY MANAGEMENT

15.1 STATEMENT OF COMPLIANCE

This clinical study is designed to be in compliance with the ethical principles in the Declaration of Helsinki, with the ICH guidelines for Good Clinical Practice (GCP), with the University of

EX-MKTG-148 SUN Protocol v1.5 23Feb2023

Waterloo's Guidelines for Research with Human Participants and with the Tri-Council Policy Statement: Ethical Conduct for Research Involving Humans, 2nd Edition.

- Declaration of Helsinki
- ICH E6 International Council for Harmonisation of Technical Requirements for Pharmaceuticals for Human Use Guidelines for Good Clinical Practice
- Tri-Council Policy Statement: Ethical Conduct for Research Involving Humans TCPS 2 (2018)
- https://uwaterloo.ca/research/office-research-ethics/research-human-participants

Informed consent shall be obtained in writing from the participant and the process shall be documented before any procedure specific to the clinical investigation is carried out.

15.2 ETHICS REVIEW

This protocol will be submitted to and reviewed through the Sterling Institutional Review Board. Notification of ethics clearance of the application is required prior to the commencement of the study.

This study will be conducted in accordance with Institutional Review Board regulations (U.S. 21CFR Part 56.103) or applicable IEC regulations. Copies of all IRB/IEC correspondence with the investigator/sponsor will be kept on file. The study will commence upon approval from the following Institutional Review Board: Sterling Institutional Review Board; Telephone number: [contact] and email address: [contact].

15.3 CLINICAL TRIAL REGISTRATION

CooperVision will register this study with clinical trials.gov in accordance with section 801 of the Food and Drug Administration (FDA) Act which mandates the registration of certain clinical trials of drugs and medical devices. They will maintain the information on that site.

15.4 PROTOCOL DEVIATIONS

Protocol deviations are unanticipated or unintentional changes to a study after it has received prior sponsor approval and ethics clearance. Protocol deviations can be major or minor.

15.4.1 MAJOR PROTOCOL DEVIATIONS

Major protocol deviations may impact the research protocol, information consent document or other study materials, usually cannot be anticipated ahead of time and are often necessary to ensure the safety and welfare of the participants.

The following are examples of major (significant) protocol deviations:

- Changes in procedures initiated to eliminate immediate risks/hazards to participants;
- Enrollment of participants outside the protocol inclusion/exclusion criteria whether agreed to or not by the sponsor;
- Medication / device / intervention errors (i.e. incorrect drug or dosage of drug / incorrect contact lens(es) dispensed / incorrect care system dispensed);
- Inadvertent deviation in specific research intervention procedures or timing of the research intervention which could impact upon the safety or efficacy of the study-related intervention or upon the experimental design;
- Information consent documentation violations: no documentation of informed consent; incorrect version of, or incomplete, informed consent documentation used.

15.4.2 MINOR PROTOCOL DEVIATIONS

The following are examples of protocol deviations that are typically considered minor:

- Logistical or administrative aspects of the study (e.g., study participant missed appointment, change in appointment date);
- Inadvertent deviation in specific research intervention procedures or timing of the research intervention which would not impact upon the safety or efficacy of the studyrelated intervention or upon the experimental design (i.e., missing a measurement during a session that is not considered critical for the study).

15.4.3 REPORTING AND DOCUMENTING PROTCOL DEVIATIONS

Major protocol deviations must be reported to the Sterling Institutional Review Board within 10 days of the deviation occurring (or its discovery) using the Reportable Events Form. To facilitate timely reporting to the sponsor, all sites must notify CORE of a major protocol deviation as soon as possible.

All protocol deviations (major and minor) occurring during the study will be documented and included in the final report.

15.5 PREMATURE TERMINATION OF THE STUDY

The sponsor, CORE or Sterling Institutional Review Board may terminate the study at any time for any reason.

15.6 STUDY PARTICIPANT RECORDS

Study participant records will be completed to comply with GCP guidelines. Records will contain:

- Unique study acronym and/or code;
- Participant ID;
- Date enrolled;
- Confirmation by investigator that participant met eligibility criteria;
- Confirmation that participant received a signed and dated copy of informed consent;
- Exit date;
- Investigator's signature confirming study exit.

An enrolment log will be maintained which will list all participants who attended for a screening visit.

15.7 RETENTION OF STUDY RECORDS AND DATA

When the study has been completed, all sites will send the original study product accountability and dispensing logs, and enrolment logs to CORE. Each site should retain the original consent documents and the study data collection forms documentation for ten years following the close of the database in case data queries arise during the analysis and report writing stages. CORE may request that these originals be sent to them for storage.

Records and data from this study will be retained at CORE for a minimum of 25 years. Details regarding storage procedures are given in CORE SOP014 Clinical data management.

16 REPORT

A report will be sent to the sponsor by CORE according to terms described in the study contract.
